10.7 Sample Size

Twenty-four evaluable patients will be enrolled. If the rate of enrolled patients who underwent ASCT and do not receive lenalidomide is about 15% then at least 28 patients may need to be enrolled. Regimens of high dose chemotherapy and ASCT for high risk (PET positive) lymphomas have historically produced a PFS12 of <10%. Single agent lenalidomide in relapsed/refractory lymphomas has been shown to produce a PFS12 of approximately 30%. The use of lenalidomide after high dose chemotherapy and ASCT will be considered worthy of further development if the PFS12 is 30% and will be considered not worthy of further development if the PFS12 is 10%. A total of 24 evaluable patients will provide 89% power for an exact test for a single proportion, with null rate of no interest (π_0) of 10%, alternative rate of interest (π_A) of 30%, at one-sided type I error (α) = 10%. A one-sided test is appropriate for early phase trials seeking to detect an improvement over historical rates.

10.8 Study Duration

Assuming that lenalidomide at 10 mg will be feasible and an accrual rate of 8-10 patients per year, accrual will continue for initial 36 months. PFS12 will be evaluated 12 months after end of accrual. Lenalidomide maintenance will continue for up to 24 months after the end accrual. The total duration of the study will be up to 60 months.

11 Regulatory Considerations

11.1 Institutional Review Board/Clinical Trials Scientific Review and Monitoring Committee Approval

The protocol for this study has been designed in accordance with the general ethical principles outlined in the Declaration of Helsinki. The review of this protocol by the IRB/CTSRMC and the performance of all aspects of the study, including the methods used for obtaining informed consent, must also be in accordance with principles enunciated in the declaration, as well as ICH Guidelines, Title 21 of the Code of Federal Regulations (CFR), Part 50 Protection of Human Subjects and Part 56 Institutional Review Boards.

The Investigator will be responsible for preparing documents for submission to the relevant IRB/CTSRMC and obtaining written approval for this study. The approval will be obtained prior to the initiation of the study.

The approval for both the protocol and informed consent must specify the date of approval and version date.

Any amendments to the protocol after receipt of IRB/CTSRMC approval must be submitted by the Investigator to the IRB/CTSRMC for approval.

Any advertisements used to recruit subjects for the study must be reviewed and approved by the IRB/CTSRMC prior to use.

11.2 Informed Consent

The Investigator must obtain informed consent of a subject or his/her designee prior to any study related procedures as per GCPs as set forth in the CFR and ICH guidelines.

Documentation that informed consent occurred prior to the subject's entry into the study and the informed consent process should be recorded in the subject's source documents. The original consent form signed and dated by the subject and by the person consenting the subject prior to the subject's entry into the study, must be maintained in the Investigator's study files.

11.3 Subject Confidentiality

Celgene affirms the subject's right to protection against invasion of privacy. In compliance with United States federal regulations, Celgene requires the Investigator to permit representatives of Celgene Corporation and, when necessary, representatives of the FDA or other regulatory authorities to review and/or copy any medical records relevant to the study in accordance with local laws.

Should direct access to medical records require a waiver or authorization separate from the subject's statement of informed consent, it is the responsibility of the Investigator to obtain such permission in writing from the appropriate individual.

11.4 Study Records Requirements

The Investigator must ensure that the records and documents pertaining to the conduct of the study and the distribution of the protocol therapy, that is copies of CRFs and source documents (original documents, data, and records [e.g., hospital records; clinical and office charts; laboratory notes; memoranda; subject's diaries or evaluation checklists; SAE reports, pharmacy dispensing records; recorded data from automated instruments; copies or transcriptions certified after verification as being accurate copies; microfiches; photographic negatives, microfilm, or magnetic media; x-rays; subject files; and records kept at the pharmacy, at the laboratories, and at medico-technical departments involved in the clinical study; documents regarding subject treatment and drug accountability; original signed informed consents, etc.]) be retained by the Investigator for as long as needed to comply with national and international regulations (generally 2 years after discontinuing clinical development or after the last marketing approval). The Investigator agrees to adhere to the document/records retention procedures by signing the protocol.

11.5 Premature Discontinuation of Study

The Principal Investigator, institution and Celgene have the right to discontinue this study at any time for reasonable medical or administrative reasons. Possible reasons for termination of the study could be but are not limited to:

- Unsatisfactory enrollment with respect to quantity or quality.
- Inaccurate or incomplete data collection.
- Falsification of records.
- Failure to adhere to the study protocol.

Any possible premature discontinuation would be documented adequately with reasons being stated, and information would have to be issued according to local requirements (e.g., IRB/EC, regulatory authorities, etc.).

Appendices

Appendix A: Risks of Fetal Exposure, Pregnancy Testing Guidelines and Acceptable Birth Control Methods

Risks Associated with Pregnancy

The use of lenalidomide in pregnant females and nursing mothers has not been studied nor has the effect of the lenalidomide on human eggs and sperm. Lenalidomide is structurally related to thalidomide. Thalidomide is a known human teratogenic active substance that causes severe life-threatening birth defects. An embryofetal development study in animals indicates that lenalidomide produced malformations in the offspring of female monkeys who received the drug during pregnancy. The teratogenic effect of lenalidomide in humans cannot be ruled out. Therefore, a risk minimization plan to prevent pregnancy must be observed.

All study participants must be registered into the mandatory Revlimid REMS® program, and be willing and able to comply with the requirements of Revlimid REMS®.

Criteria for females of childbearing potential (FCBP)

This protocol defines a female of childbearing potential as a sexually mature female who: 1) has not undergone a hysterectomy or bilateral oophorectomy or 2) has not been naturally postmenopausal for at least 24 consecutive months (i.e., has had menses at any time in the preceding 24 consecutive months).

The investigator must ensure that:

- Females of childbearing potential comply with the conditions for pregnancy risk minimization, including confirmation that she has an adequate level of understanding
- Females NOT of childbearing potential acknowledge that she understands the hazards and necessary precautions associated with the use of lenalidomide
- Male patients taking lenalidomide acknowledge that he understands that traces of lenalidomide have been found in semen, that he understands the potential teratogenic risk if engaged in sexual activity with a female of childbearing potential, and that he understands the need for the use of a condom even if he has had a vasectomy, if engaged in sexual activity with a female of childbearing potential.

Contraception

Females of childbearing potential (FCBP) enrolled in this protocol must agree to use two reliable forms of contraception simultaneously or to practice complete abstinence from heterosexual intercourse during the following time periods related to this study: 1) for at least 28 days before starting lenalidomide; 2) throughout the entire duration of lenalidomide treatment; 3) during dose interruptions; and 4) for at least 28 days after lenalidomide discontinuation.

The two methods of reliable contraception must include one highly effective method and one additional effective (barrier) method. FCBP must be referred to a qualified provider of contraceptive methods if needed. The following are examples of highly effective and additional effective methods of contraception:

- Highly effective methods:
 - Intrauterine device (IUD)
 - Hormonal (birth control pills, injections, implants)
 - Tubal ligation
 - Partner's vasectomy
- Additional effective methods:
 - Male condom
 - Diaphragm
 - Cervical Cap

Because of the increased risk of venous thromboembolism in patients with multiple myeloma taking lenalidomide and dexamethasone, combined oral contraceptive pills are not recommended. If a patient is currently using combined oral contraception the patient should switch to one of the effective method listed above. The risk of venous thromboembolism continues for 4–6 weeks after discontinuing combined oral contraception. The efficacy of contraceptive steroids may be reduced during co-treatment with dexamethasone.

Implants and levonorgestrel-releasing intrauterine systems are associated with an increased risk of infection at the time of insertion and irregular vaginal bleeding. Prophylactic antibiotics should be considered particularly in patients with neutropenia.

Pregnancy testing

Medically supervised pregnancy tests with a minimum sensitivity of 50 mIU/mL must be performed for females of childbearing potential, including females of childbearing potential who commit to complete abstinence, as outlined below.

Before Starting Lenalidomide

Female Patients:

FCBP must have two negative pregnancy tests (sensitivity of at least 50 mIU/mL) prior to prescribing lenalidomide. The first pregnancy test must be performed within 10-14 days prior to prescribing lenalidomide and the second pregnancy test must be performed within 24 hours prior to prescribing lenalidomide. The patient may not receive lenalidomide until the Investigator has verified that the results of these pregnancy tests are negative.

Male Patients:

Must agree to practice complete abstinence or agree to use a condom during sexual contact with pregnant females or females of childbearing potential throughout the entire duration of lenalidomide treatment, during dose interruptions and for at least 28 days following lenalidomide discontinuation, even if he has undergone a successful vasectomy.

During Study Participation and for 28 days Following Lenalidomide Discontinuation***Female Patients:***

- FCBP with regular or no menstrual cycles must agree to have pregnancy tests every 28 days throughout the duration of lenalidomide treatment, including dose interruptions, at lenalidomide discontinuation, and at Day 28 following lenalidomide discontinuation. If menstrual cycles are irregular, the pregnancy testing must occur weekly every 14 days throughout the duration of lenalidomide treatment, including dose interruptions, at lenalidomide discontinuation, and at Day 28 following lenalidomide discontinuation.
- At each visit, the Investigator must confirm with the FCBP that she is continuing to use two reliable methods of birth control at each visit during the time that birth control is required.
- If pregnancy or a positive pregnancy test does occur in a study patient, lenalidomide must be immediately discontinued.
- Pregnancy testing and counseling must be performed if a patient misses her period or if her pregnancy test or her menstrual bleeding is abnormal. Lenalidomide treatment must be temporarily discontinued during this evaluation.
- Females must agree to abstain from breastfeeding during study participation and for at least 28 days after lenalidomide discontinuation.

Male Patients:

- Must practice complete abstinence or use a condom during sexual contact with pregnant females or females of childbearing potential throughout the entire duration of lenalidomide treatment, during dose interruptions and for at least 28 days following lenalidomide discontinuation, even if he has undergone a successful vasectomy.
- If pregnancy or a positive pregnancy test does occur in the partner of a male study patient during study participation, the investigator must be notified immediately.

Additional precautions:

- Patients should be instructed never to give lenalidomide to another person.
- Female patients should not donate blood during therapy and for at least 28 days following discontinuation of lenalidomide.
- Male patients should not donate blood, semen or sperm during therapy or for at least 28 days following discontinuation of lenalidomide.
- Only enough lenalidomide for one cycle of therapy may be prescribed with each cycle of therapy.

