* Variations of ± 7 days of scheduled visits are permitted; in rare circumstances, the study calendar may be recalculated to accommodate for a change in study visits out of this window (due to transportation issues, weather events, etc.) at the discretion of the treating physician.

[^] To be performed within 7 days of day 1 of lenalidomide therapy. If Screening physical examination, vital signs, weight, labs and ECOG performance status were done within 7 days of Day 1, they do not need to be repeated at this timepoint.

An unscheduled visit can occur at any time during the study. Source must be maintained for these unscheduled visits. The date for the visit and any data generated must be recorded on the appropriate CRF. Source documents for these unscheduled visits must also be maintained.

¹ To include Thyroid Stimulating Hormone (TSH) at Screening B, at treatment discontinuation, and whenever clinically indicated. T3 and T4 levels may be assessed as clinically indicated. If HIV and Hepatitis B status are unknown (unlikely since all patients undergoing ASCT are screened), then these tests will be sent at Screening B.

² Pregnancy tests for females of childbearing potential. A female of childbearing potential (FCBP) is a sexually mature female who: 1) has not undergone a hysterectomy or bilateral oophorectomy; or 2) has not been naturally postmenopausal for at least 24 consecutive months (i.e., has had menses at any time in the preceding 24 consecutive months).

³ Pregnancy tests must occur within 10 – 14 days and again within 24 hours prior to prescribing lenalidomide for Cycle 1 (prescriptions must be filled within 7 days). FCBP with regular or no menstruation must have a pregnancy test every 28 days while on therapy (including breaks in therapy); at discontinuation of lenalidomide, and at Day 28 post the last dose of lenalidomide. If menstrual cycles are irregular, the pregnancy testing must occur weekly every 14 days throughout the duration of lenalidomide treatment, including dose interruptions, at lenalidomide discontinuation, and at Day 28 following lenalidomide discontinuation (see Appendix A: Risks of Fetal Exposure, Pregnancy Testing Guidelines and Acceptable Birth Control Methods).

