⁴ Progression will be determined by the treating physician as based on clinical picture and radiographic findings. The initial imaging will be performed after ASCT, but prior to initiating maintenance lenalidomide therapy. During the maintenance phase, imaging (PET/CT or CT scan) will be performed every 3 months during the first year and every 4 months during the second year of maintenance. Imaging studies after the second year of maintenance will be at discretion of treating physician. During the first cycle of maintenance therapy, there will be two visits with physical exam. Then, participants will be seen on day 1 of each subsequent cycle. It will not be required to document progression by tissue biopsy (it will be at discretion of treating physician).

⁵ An additional safety assessment will be done 28 days (+/- 7 days) following the last dose of protocol therapy.

⁶ If screening assessments were done within 7 days of Day 1, they do not need to be repeated at Study Day 1.

⁷ Lenalidomide must be prescribed through and in compliance with Celgene's Revlimid REMS® program. Prescriptions must be filled within 14 days, unless the patient is a female of childbearing potential, in which case the prescription must be filled within 7 days. Consideration should be given to prescribing lenalidomide 5 to 7 days in advance of Day 1 of each cycle to allow time for required patient and prescriber surveys, and drug shipment to patient. Any unused Revlimid® (lenalidomide) should be returned to the patient for disposition in accordance with the Revlimid REMS® program.

⁸ Subjects will be followed every 3 months for the first 3 years after discontinuation of protocol therapy, and then annually thereafter; those patients who did not achieve hematological recovery by Day 100 after ASCT and never started on lenalidomide maintenance will also be followed every 3 months for the first year and then annually for anti-cancer treatment and progression/survival information.

3 Background and Rationale

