13. Females of childbearing potential (FCBP)[†] must have a negative serum or urine pregnancy test with a sensitivity of at least 50 mIU/mL within 10 – 14 days and again within 24 hours prior to prescribing lenalidomide for Cycle 1 (prescriptions must be filled within 7 days) and must either commit to continued abstinence from heterosexual intercourse or begin TWO acceptable methods of birth control, one highly effective method and one additional effective method AT THE SAME TIME, at least 28 days before she starts taking lenalidomide. FCBP must also agree to ongoing pregnancy testing. Men must agree to use a latex condom during sexual contact with a FCBP even if they have had a successful vasectomy. See Appendix: Risks of Fetal Exposure, Pregnancy Testing Guidelines and Acceptable Birth Control Methods.
14. Able to take aspirin (81 or 325 mg) daily as prophylactic anticoagulation (warfarin or low molecular weight heparin may be used for patients intolerant of aspirin or at the discretion of the treating physician).

5.2.2 Exclusion criteria:

1. A PET/CT or CT scan post-ASCT which shows disease progression.
2. Any serious medical condition, laboratory abnormality, or psychiatric illness that would prevent the subject from signing the informed consent form.
3. Pregnant or breast feeding females (lactating females must agree not to breast feed while taking lenalidomide).
4. Any condition, including the presence of laboratory abnormalities, which places the subject at unacceptable risk if he/she were to participate in the study or confounds the ability to interpret data from the study.
5. Use of any other experimental drug or therapy within 28 days of initiating treatment with lenalidomide.
6. Known hypersensitivity to thalidomide.
7. The development of erythema nodosum, a blistering or desquamating rash, while taking thalidomide or similar drugs.
8. Any prior use of lenalidomide.
9. Concurrent use of other anti-cancer agents or therapies during study treatment.
10. Known seropositive for or active viral infection with human immunodeficiency virus (HIV) or hepatitis B virus (HBV). Patients who are seropositive because of hepatitis B virus vaccine are eligible.

[†] A female of childbearing potential is a sexually mature female who: 1) has not undergone a hysterectomy or bilateral oophorectomy; or 2) has not been naturally postmenopausal for at least 24 consecutive months (i.e., has had menses at any time in the preceding 24 consecutive months).

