5.3 Visit Schedule and Assessments

5.3.1 Screening/Enrollment - to take place at the time of hematologic recovery, between Days 28-100 post ASCT and within 28 days of initiation of treatment with lenalidomide:

- Review and signing of the Informed Consent Form
- Complete medical history, including prior and current medications, treatments, and anti-cancer therapies.
- Physical Exam and evaluation of ECOG PS
- Vital signs, including blood pressure, heart rate, oral temperature and weight
- Imaging with PET/CT scan or CT scan
- Electrocardiogram
- Serum Chemistry panel including sodium, potassium, chloride, CO₂, calcium, serum creatinine, BUN, total bilirubin, alkaline phosphatase, AST, ALT and TSH
- For women of childbearing potential, a serum pregnancy test must be performed 10-14 days and then within 24 hours prior to initiating treatment with lenalidomide
- Registration into Revlimid REMS® program

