5.3.4 Cycles 2-24, Day 1 (+/- 7 days)

- Physical Examination and evaluation of ECOG PS
- Vital signs: blood pressure, heart rate, temperature and weight
- CBC with differential and platelets
- Serum Chemistry panel including sodium, potassium, chloride, CO₂, calcium, serum creatinine, BUN, total bilirubin, alkaline phosphatase, AST, ALT
- Serum pregnancy test (for women of child-bearing potential)
- Review of interim adverse events and concomitant medications

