5.3.6 Study Discontinuation

The following will be performed at the time of study discontinuation, whether due to study completion or early withdrawal from study participation

- Physical Exam and evaluation of ECOG PS
- Vital signs (Blood pressure, heart rate, temperature, weight)
- CBC with differential and platelets
- Serum chemistry panel including sodium, potassium, chloride, CO₂, calcium, serum creatinine, BUN, total bilirubin, alkaline phosphatase, AST, ALT and TSH
- Assessment of adverse events and concomitant medications

5.3.7 Safety Assessment (to be performed 28 Days (+/- 7 days) after study discontinuation)

- Assessment of adverse events and concomitant medications

5.3.8 Follow-Up (to be performed every 3 months for the first 3 years after study discontinuation, and then yearly thereafter)

- Review of anti-cancer treatments
- Review of progression and survival information

Assessments to be performed at screening and during scheduled study visits are also outlined in Section 2 Table of Study Assessments.

At treatment discontinuation, subjects will undergo off study evaluations per the Schedule of Assessments, Section 2. In addition, a safety assessment will be done approximately 28 days after the last dose of protocol therapy. Follow-up contact with the subjects should occur at a minimum of 3 months during the first 3 years after finishing maintenance phase and annually after that.

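### For women with irregular cycles, the protocol gives two pregnancy-test intervals in one phrase, and its visit lists meet neither

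*Combined protocol and SAP*

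**What the plan says.** **Interval on treatment.** For regular or absent cycles, Appendix A is plain: "FCBP with regular or no menstrual cycles must agree to have pregnancy tests every 28 days throughout the duration of lenalidomide treatment". For irregular cycles, footnote 3 to the Section 2 schedule reads "If menstrual cycles are irregular, the pregnancy testing must occur weekly every 14 days throughout the duration of lenalidomide treatment", and Appendix A uses the same words: "the pregnancy testing must occur weekly every 14 days throughout the duration of lenalidomide treatment". Both places also require a test at discontinuation and another at Day 28 afterwards.

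**Visit lists.** Section 5.3.3 has a test for women with irregular menses at Cycle 1 Day 15 and none at Day 22. Section 5.3.4 has one test per cycle, on Day 1, for all women of childbearing potential. The Section 2 grid marks screening, Cycle 1 Day 1, Day 1 of Cycles 2-24 and discontinuation; Cycle 1 Days 15 and 22 are blank. Section 5.3.6 names no pregnancy test, and the whole content of the 28-day visit in 5.3.7 is "Assessment of adverse events and concomitant medications".

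**Second pre-treatment test.** Inclusion criterion 13 requires it "within 24 hours prior to prescribing lenalidomide for Cycle 1"; footnote 3 and Appendix A also tie it to prescribing. Sections 5.3.1 and 5.3.3 instead say "a serum pregnancy test must be performed 10-14 days and then within 24 hours prior to initiating treatment with lenalidomide". Footnote 7 adds: "Consideration should be given to prescribing lenalidomide 5 to 7 days in advance of Day 1 of each cycle". Footnote 6, which is attached to the Day 1 pregnancy-test cell, waives a Day 1 repeat when the screening assessment was done within 7 days.

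**The concern.** Appendix A accepts that a teratogenic effect in humans is possible and makes a pregnancy-prevention plan mandatory. Testing is part of that plan, so the interval is a binding safety instruction. A coordinator who works from the Section 5.3 lists would give a woman with irregular cycles fewer tests than either interval requires. Someone who turns to footnote 3 or Appendix A to settle the matter meets the same double interval in both. The protocol gives no order of precedence, so neither site staff nor an auditor can say which interval is binding.

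**Working it through.** No figure in the plan needs to be reproduced; the check is a count of scheduled tests and a comparison of passages.

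**Inputs.** Section 5.1 gives 24 cycles of 28 days, so 24 × 28 = 672 days. The intervals come from footnote 3 and Appendix A, and the scheduled visits from Sections 5.3.3 and 5.3.4 and the Section 2 grid.

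**Basis.** A woman who completes all 24 cycles without delay, tested on nominal days. One test at the start of Cycle 1 (the pre-dose test) is counted on every line. The earlier screening test, 10 to 14 days before, is left out on every line.

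| Source | Cycle 1 pre-dose | Cycle 1, later | Cycles 2-24 | Total |
|---|---|---|---|---|
| Irregular, read as weekly | 1 | 3 (Days 8, 15, 22) | 23 × 4 = 92 | 96 (= 672/7) |
| Irregular, read as every 14 days | 1 | 1 (Day 15) | 23 × 2 = 46 | 48 (= 672/14) |
| Regular or absent cycles, every 28 days | 1 | 0 | 23 × 1 = 23 | 24 (= 672/28) |
| Section 5.3 lists, irregular cycles | 1 | 1 (Day 15) | 23 | 25 |
| Section 2 grid cells | 1 | 0 | 23 | 24 |

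The Section 5.3 lists fall short by 96 − 25 = 71 tests on the weekly reading and by 48 − 25 = 23 on the 14-day reading. They provide 25/96 = 26% and 25/48 = 52% of the tests. On the 14-day reading the 23 missing tests are exactly the mid-cycle tests of Cycles 2-24. In effect, 5.3.3 and 5.3.4 apply the 28-day schedule to everyone and add one test, in Cycle 1, for irregular cycles.

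**End of treatment.** Footnote 3 and Appendix A add two tests, giving 98, 50 and 26 on the first three lines. Sections 5.3.6 and 5.3.7 name neither, so the Section 5.3 total stays at 25. The grid cells mark discontinuation but not Day 28: 24 + 1 = 25.

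**Second pre-treatment test.** Under footnote 7's suggestion, prescribing falls 5 to 7 days before Day 1. A test within 24 hours before prescribing is then about 5 to 8 days old on Day 1 and cannot also be within 24 hours of starting. Footnote 6 separately accepts a Day 1 test up to 7 days old, against the 24 hours in 5.3.3. Section 5.3.3 grants the 7-day waiver to the examination, vital signs, blood count and chemistry, but not to the pregnancy test, so the grid and the list disagree on this item.

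**The case against.** The strongest reply is that Section 2 governs and is nearly complete. Footnote 3 belongs to the grid's pregnancy row and carries the irregular-cycle rule and both end-of-treatment tests. The grid marks discontinuation, and both the text after 5.3.8 and Section 5.8 send staff to Section 2 for off-study evaluations. This stands for the end of treatment: a reader might infer that those tests are missing from the protocol, and they are not. Only the 5.3.6 and 5.3.7 lists and the grid's Day 28 cell are incomplete. The reply does not settle the interval, because footnote 3 is itself one of the two places with the double wording.

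Second, a weekly schedule also satisfies a 14-day rule, so the text can be carried out. That is correct, and it rules out the stronger reading that the testing rule as a whole cannot be followed. It does not tell staff which frequency is required, and the visit lists meet neither.

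Third, words may have dropped out between the two intervals, for instance in a two-stage rule. Identical wording in two separate places makes a random reading error unlikely. Any mixture of the two intervals would give between 48 and 96 tests, still above 25.

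Fourth, testing once before prescribing and again before starting satisfies both timings, and footnote 7 is only a suggestion. This stands, and it makes the timing point secondary. Footnote 6's waiver still conflicts with 5.3.3.

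Fifth, everyone must comply with the Revlimid REMS program. The documents do not state that program's test intervals, so whether it would close the gap in practice cannot be checked here.

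A reader might also see a conflict between serum only in the visit lists and serum or urine in criterion 13. There is none: a serum test satisfies both.

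**Conclusion.** The inconsistency holds for women of childbearing potential with irregular cycles. Two intervals are stated together in two places, and Section 5.3 schedules 25 tests over 672 days against 96 or 48. The counts assume full treatment without delays or unscheduled tests; the documents do not say how many participants would be in this group. The incomplete end-of-treatment lists and the differing timing of the second pre-treatment test are secondary.

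The 28-day interval for regular or absent cycles is clear, and the visit lists match it during treatment (24 tests by either count). The omissions in 5.3.6 and 5.3.7 do concern all women of childbearing potential. This is an internal inconsistency in a safety procedure, not a design choice, and it does not touch the DLT, PFS or OS analyses.

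**What to change.** Reconcile footnotes 3 and 6, Appendix A, inclusion criterion 13 and Sections 5.3.1 to 5.3.7 so that they state one interval for irregular cycles and one timing for the second pre-treatment test, and say whether footnote 6's waiver applies to that test. Then enter the resulting mid-cycle, discontinuation and Day 28 tests in the Section 5.3 lists and the Section 2 grid cells, including Cycle 1 Day 15. The choice of interval and timing belongs to the investigator and sponsor.

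The cost is wording in an amendment. It adds no tests beyond those the reconciled rule requires, and no change to sample size or analysis.
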